**Duration of treatment/Study participation:**

Patients will receive study drug in this study for up to 52 weeks (non-responders) or a maximum of 108 weeks (responders).

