## 6. STUDY OBJECTIVES

The overall objectives of the study are to evaluate long-term safety of CTP-543 and to assess long-term effects of CTP-543 on treating hair loss in adult patients with moderate to severe alopecia areata.

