### 6.1. Study Design and Method of Treatment Assignment

Patients with alopecia areata who previously participated in a qualifying Phase 3 clinical trial (CP543.3001 or CP543.3002) with CTP-543 and who complete a 24-week Treatment Period on Study Medication (active or placebo), have the opportunity to enroll in this open-label extension study. At the Week 52 visit, patients will be assessed for treatment success (Responders) defined as patients having an absolute SALT score of  $\leq 20$  at Week 52. These Responders will be eligible to continue in the OLE extension for up to a maximum of one additional year. Non-responders will complete the study at Week 52. Patients will provide informed consent prior to any baseline assessments being performed. Drug will be dispensed to patients following confirmation of eligibility.

Initially, patients were assigned to receive daily treatment with CTP-543 at a dose of 8 mg BID or 12 mg BID according to the following criteria:

| Previous Treatment in Qualifying Trial | Treatment Assignment in OLE |
|--|-----------------------------|
| Placebo BID                            | 8 mg BID or 12 mg BID       |
| 8 mg BID                               | 8 mg BID                    |
| 12 mg BID                              | 12 mg BID                   |

Placebo patients were randomized via the study Interactive Web Response System (IWRS) in a 1:1 ratio to 8 mg BID or 12 mg BID. The randomization schedule was generated prior to subject enrollment from studies CP543.3001 and CP543.3002.

Following reports of thrombosis with 12 mg BID after long-term administration of CTP-543 and discussions with the US Food and Drug Administration (FDA), the 12 mg BID dose was immediately discontinued and communicated under an Urgent Safety Measure. Due to implementation of this urgent safety measure, all patients previously assigned to the 12 mg BID dose will be dose reduced to the 8 mg BID dose, should they elect to continue in the trial, for the duration of the trial up to a total of 52 weeks for non-responders or a maximum of 108 weeks for responders.

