#### **11.2.3.1. Adverse Events**

Treatment-emergent adverse events (TEAEs) will be defined as any adverse event that occurs after administration of the first dose of study drug until completion of the study or the Early Termination Visit. The number and percentage of patients who report TEAEs will be summarized by system organ class and preferred term.

Treatment emergent adverse events will also be summarized by intensity as well as relationship to study drug.

Patients who report the same preferred term on multiple occasions will be counted once for the preferred term: under the highest severity when summarized by severity and under the closest relationship to study drug when summarized by relationship. If a patient reports multiple preferred terms for a system organ class, the patient will be counted only once for that system organ class.

The number and percentage of patients who experience TEAEs will be summarized by dosing regimen for the following:

- By system organ class and preferred term
- By severity/intensity, system organ class, and preferred term
- By relationship to study drug, system organ class, and preferred term
- Serious adverse events by system organ class and preferred term
- Serious adverse events by relationship to study drug, system organ class, and preferred term

- Adverse events resulting in discontinuation of study drug by system organ class and preferred term
- Adverse events that result in study drug dose interruption by system organ class and preferred term

By-patient listings will be provided for any deaths, serious adverse events, and adverse events leading to discontinuation of treatment.

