9.3. Adverse Events

An AE is any untoward medical occurrence that may appear or worsen in a subject during the course of a study. It may be a new intercurrent illness, a worsening concomitant illness, an injury, or any concomitant impairment of the subject's health, including laboratory test values, regardless of etiology. Any worsening (i.e., any clinically significant adverse change in the frequency or intensity of a pre-existing condition) should be considered an AE. A diagnosis or syndrome should be recorded on the AE page of the eCRF rather than the individual signs or symptoms of the diagnosis or syndrome. A worsening of the condition under study, alopecia areata, will not be reported as an AE.

All subjects will be monitored for AEs during the study. Assessments may include monitoring of the following parameters: the subject's clinical symptoms, laboratory, physical examination findings, or findings from other tests and/or procedures.

AEs will be coded using MedDRA version 23.1 and summarized by treatment group, system organ class, and preferred term.

An AE with a start date before the date of the first dose of study drug in CP543.5002 (i.e., generally Day 1), will be considered a pre-treatment AE. TEAEs will be defined as any AE that occurs on or after the day of administration of the first dose of study drug. Non-serious AEs are collected until completion of the study or the Early Termination Visit. Serious adverse events are reported through 30 days beyond the last dose of study drug. The number and percentage of subjects who report TEAEs will be summarized by treatment group, system organ class, and preferred term.

If a subject changes dose during the study, AEs will be considered treatment-emergent with respect to the most recent dose taken prior the start of the AE and will be tabulated under that treatment column. This may result in some subjects being included in more than one treatment column.

TEAEs will also be summarized by intensity as well as relationship to study drug.

Partial dates will be imputed for the purposes of defining TEAEs as follows:

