- For a missing start day where the month and year are present, the start day will be set to the first day of the month, unless 1) the first day of the month is before the date of administration of study drug and the month and year are the same as the month and year of the date of administration of study drug, and 2) the end date is on or after the date of administration of study drug or the end date is completely missing, in which case the start day will be set to the first day of administration of study drug.
- For a missing start day and month where the year is present, the start day and month will be set to January 1st, unless 1) January 1st is before the date of administration of study drug, and 2) the end date is on or after the date of administration of study drug or the end date is completely missing, in which case the start day and month will be set to that of the first date of administration of study drug.

Sun Pharmaceutical Industries, Inc.
Statistical Analysis Plan – CP543.5002

- For a missing end day where the month and year are present, the end day will be set to the last day of the month, unless the month and year are the same as the month and year of the last visit date for the subject, in which case the end day will be set to that of the subject's last visit date.
- For a missing end day and month where the year is present, the end day and month will be set to the subject's last visit date, unless the year of the subject's last visit date is greater than the end year, in which case the end day and month will be set to December 31st.

For an entirely missing start date, the adverse event will be deemed treatment emergent unless the end date is before the first date of administration or, in the case of a partial end date, it is clear from the available date parts that the end date is prior to the date of administration.

Subjects who report the same preferred term on multiple occasions will be counted once for the preferred term: under the highest severity when summarized by severity and under the closest relationship to study drug when summarized by relationship. Missing severity or relationship will not be imputed. If a subject reports multiple preferred terms for a system organ class, the subject will be counted only once for that system organ class.

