An overall TEAE summary table by treatment group and overall with the total number of TEAEs and the number and percentage of subjects with at least one of the following will be presented: TEAE, serious TEAE, serious related TEAE, TEAE leading to study drug interruption, TEAE leading to dose reduction, TEAE leading to study discontinuation, TEAE leading to death, mild TEAE (CTCAE grade 1), moderate TEAE (CTCAE grade 2), severe TEAE (CTCAE grade 3 or above), mild related TEAE (CTCAE grade 1), moderate related TEAE (CTCAE grade 2), severe related TEAE (CTCAE grade 3 or above), related TEAE, possibly related TEAE, probably related TEAE, definitely related TEAE, not related TEAE, unlikely related TEAE, related serious TEAE, possibly related serious TEAE, probably related serious TEAE, definitely related serious TEAE, not related serious TEAE, unlikely related serious TEAE. “Related” TEAEs will be defined as TEAEs which the study investigator has categorized as possibly, probably, or definitely related to study drug. “Not related” TEAEs will be defined as TEAEs which the study investigator has categorized as unlikely or not related to study drug. “Related” serious TEAEs and “not related” serious TEAEs will be defined analogously for serious TEAEs. For each severity category, the subject will be counted once at the subject’s maximum level of severity. For each relatedness category, subjects will be counted once at the subject's maximum level of relatedness.

The number and percentage of subjects who experience TEAEs and the total number of TEAEs will be summarized by treatment group and overall for the following:

- By system organ class and preferred term
- By severity/intensity (mild [CTCAE grade 1], moderate [CTCAE grade 2], or severe [CTCAE grade 3 or above]), system organ class, and preferred term
- By maximum severity/intensity (mild [CTCAE grade 1], moderate [CTCAE grade 2], or severe [CTCAE grade 3 or above]), system organ class, and preferred term
- By relationship to study drug, system organ class, and preferred term

Sun Pharmaceutical Industries, Inc.
Statistical Analysis Plan – CP543.5002

- By maximum relationship to study drug, system organ class, and preferred term
- Serious TEAEs by system organ class and preferred term
- Serious TEAEs by relationship to study drug, system organ class, and preferred term
- Serious TEAEs by maximum relationship to study drug, system organ class, and preferred term

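### The planned adverse event summaries give one whole-study percentage per dose column, so they cannot show whether serious or thromboembolic events become more frequent with time on drug

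*Protocol*

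**What the plan says.** Protocol 6 states the purpose: "The overall objectives of the study are to evaluate long-term safety of CTP-543". Protocol 6.1 explains why the higher dose was dropped: "Following reports of thrombosis with 12 mg BID after long-term administration of CTP-543". Treatment lasts up to 52 weeks for patients who are not responders at Week 52 and at most 108 weeks for responders.

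Protocol 11.2.3.1 sets one event window: "any adverse event that occurs after administration of the first dose of study drug until completion of the study or the Early Termination Visit". SAP 9.3, which takes precedence over the protocol, also uses one window: "TEAEs will be defined as any AE that occurs on or after the day of administration of the first dose of study drug". It collects serious events to 30 days after the last dose.

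The counting rule in SAP 9.3 is the same as the protocol's: "Subjects who report the same preferred term on multiple occasions will be counted once for the preferred term". The planned measure is: "The number and percentage of subjects who experience TEAEs and the total number of TEAEs will be summarized by treatment group and overall". Under SAP 4 the default denominator is the number of subjects in the population. Under SAP 4.1 each event is assigned to the most recent dose taken before onset, so a patient who changed dose can appear in two columns.

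**The concern.** An extension adds later exposure to the 24-week qualifying trials. The safety question specific to it is whether events become more frequent the longer patients take the drug. The reason given for stopping 12 mg BID is itself about duration.

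A single percentage over the whole study cannot answer that question. It also mixes patients whose maximum follow-up differs about two-fold, and the difference depends on Week 52 response. The dose columns do not stand in for time. Once patients starting on 12 mg BID were reduced, their later events count under 8 mg BID, next to the early events of patients who started on 8 mg BID.

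If the tables stay as planned, the study report could present stable risk and rising risk in the same way.

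**Working it through.** **No plan figure to reproduce.** The documents give no sample size, event rate or hypothesis for this study. The check is an inventory of outputs followed by an illustration on stated assumptions.

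**Inventory.**
- SAP 9.3 splits events by dose column, organ class, preferred term, severity, relationship, seriousness and action taken. None of its tables is split by onset time. There is no time-to-onset summary, person-time rate or thromboembolic-event table.
- SAP 9.4 adds listings and refers back to 9.3 for serious events.
- SAP 9.2 cuts exposure into 17 duration categories (≥4 to ≥108 weeks) but does not link them to events.
- SALT, laboratory values, vital signs and ECGs are summarised by visit or scheduled assessment, and SAP 6.1 summarises time to study discontinuation. The gap is therefore specific to adverse events.

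**Unequal follow-up.** With a flat hazard of 1.0 per 100 patient-years (assumed), the expected percentage with an event is:
- 52 weeks: 1 − exp(−0.01 × 52/52.18) = 0.99%
- 108 weeks: 1 − exp(−0.01 × 108/52.18) = 2.05%

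**Illustration.** Assumed: 300 treated, 85% reaching Week 52, 45% of those continuing, 90% of them finishing, losses spread evenly, at most one serious event per patient. As a guide only, Week 24 responder rates on active drug in the qualifying trials were 29.6% to 41.5%; the Week 52 share in this study is not given.
- Patient-years before Week 52: 300 × (1 + 0.85)/2 × 52/52.18 = 276.5
- Patient-years after Week 52: 300 × 0.85 × 0.45 × (1 + 0.90)/2 × 56/52.18 = 117.0
- Doubling rate: 276.5 × 0.02 + 117.0 × 0.04 = 5.5 + 4.7 = 10.2 events, or 3.4% of 300
- Constant rate giving the same total: 10.2/393.5 = 2.6 per 100 patient-years

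| Expected events | To Week 52 | After Week 52 | Total |
|---|---|---|---|
| Rate 2.0, then 4.0 | 5.5 | 4.7 | 10.2 |
| Constant 2.6 | 7.2 | 3.0 | 10.2 |

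The totals agree by construction. The planned table and a single overall rate show only the last column; the difference is in the two columns before it. If 35% to 60% continue instead of 45%, patient-years after Week 52 are 91.0 to 156.0. That is 25% to 36% of the total, and the matching constant rate is 2.5 to 2.7.

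**Second check.** Let f be the share continuing past Week 52, with no earlier loss, T1 = 52 weeks and T2 = 56 weeks:

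crude % = 1 − exp(−h1·T1) + f·exp(−h1·T1)·(1 − exp(−h2·T2))

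Compare a flat hazard of 1.0 per 100 patient-years with a hazard of 0.5 to Week 52 that then rises. For f = 0.3, 0.4 and 0.6, a later hazard of 2.57, 2.17 and 1.78 gives the same crude percentage as the flat hazard (1.31%, 1.41% and 1.63%). The overall rate is 1.00 per 100 patient-years in both cases. A rise of 3.6- to 5.1-fold is therefore invisible to both measures.

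**What an interval table could show.** In the illustration the rate ratio is 2.0. The standard error of its log is √(1/5.5 + 1/4.7) ≈ 0.63, so the 95% CI is 2.0 ÷ and × exp(1.96 × 0.63), about 0.6 to 6.8. With 200 or 400 treated instead of 300, the intervals are about 0.4 to 9.0 and 0.7 to 5.8.

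**The case against.** The strongest case on the other side has four parts.

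- **The information exists.** Start dates are recorded for every event and all events are listed by subject. Deaths, serious events and events leading to discontinuation are also listed separately. The protocol requires withdrawal after a thromboembolic event, so each on-study case should appear in the discontinuation table and listing. With a handful of cases, individual review is realistic. This stands against the inference that the study itself cannot address duration; it can. But listings carry no number at risk, so they cannot show a rate.
- **Other analyses may cover it.** SAP 11 sends programme-wide safety to a separate integrated plan, and a sister extension of about 1,100 patients runs for up to 276 weeks. That integrated plan is not among these documents. Its analysis rests on a data freeze planned for late 2022 (SAP 8.1.2), before the dose reductions from 28 April 2023 (SAP 8.2.3.1), so it does not close the gap here.
- **The study is descriptive and allows documented post hoc work.** This is true and limits the weight of the point: the table is an addition, not the correction of an invalid analysis. A table drafted after the events are known lacks the value of one set in advance.
- **Late data will be thin and selected.** This stands. A reader might infer that first-year events swamp late ones, but in the illustration 4.7 of 10.2 events (46%) are late. A reader might also infer that an interval table would settle whether risk rises. The interval of 0.6 to 6.8 says otherwise, and later time is further selected by response, mandatory withdrawals and the dose reduction.

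**Conclusion.** The point holds for the planned summaries. Neither Protocol 11.2.3.1 nor SAP 9.3 gives an onset interval, number at risk or person-time for adverse events, and nothing else in the two documents supplies them. A two-fold rise after Week 52 in the main illustration, or a 3.6- to 5.1-fold rise in the second, would leave both the whole-study percentage and a single overall rate unchanged.

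Those sizes rest on assumed numbers treated, continuation shares and event rates, because the documents give none. The absence of any time element in the tables does not depend on them. The documents do not support saying that the data are missing, or that a better table would demonstrate or exclude rising risk.

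**What to change.** Add to SAP 9.3 a table of patients with a first TEAE, first serious TEAE and first thromboembolic event by onset interval. Count from first dose in CP543.5002, for example Weeks 0–24, >24–52 and >52–108. In each interval give the number at risk, patient-years, and the rate with 95% CI.

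Present it by dose at onset, with person-time allocated to the dose being taken, and by prior treatment (placebo or active, from the SAP 4.1 cohorts). Note that prior-active patients had already received about 24 weeks of drug. Name the terms that count as thromboembolic.

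If time since first active dose is preferred, limit it to events and person-time in CP543.5002 and use delayed entry. On that clock the responder-only period starts at about week 52 for former placebo patients and about week 24 + 52 = 76 for prior-active patients. Weeks 0–24 would then contain essentially former placebo patients only. A footnote saying that only responders remain after Week 52 is correct only on the extension clock.

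**Cost:** SAP wording, a term list and one or two tables, from dates already held. No new data or visits are needed.

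**Downside:** late cells will be sparse. Assuming 200 to 400 treated and 30% to 60% continuing, there are at most about 64 to 258 patient-years after Week 52, and zero events would still leave a 95% upper bound of about 4.7 to 1.2 per 100 patient-years. A footnote should say that the table is descriptive and that after extension Week 52 it contains responders only.

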#### **11.2.3.2. Clinical Laboratory**

Clinical laboratory variables will be presented 3 ways. First, change from Baseline to each scheduled assessment will be summarized descriptively. Baseline will be defined as the laboratory value obtained before the first dose of study drug on Day 1.

Second, treatment-emergent potentially clinically significant (PCS) laboratory values will be identified. Potentially clinically significant values are defined as those that meet Grade 3 or Grade 4 toxicity criteria from the CTCAE criteria. Treatment-emergent PCS laboratory values are those in which the Baseline value is not PCS and the post-baseline value is PCS.

Third, treatment-emergent adverse events that result in dose interruption will also be identified.

The mean change from Baseline to each scheduled assessment will be summarized descriptively by dosing regimen for each clinical laboratory variable specified in this protocol.

The number and percentage of patients with Abnormal, clinically significant laboratory values (per Investigator judgement) and the number and percentage of patients with treatment-emergent PCS laboratory values will be summarized by dosing regimen for each clinical laboratory variable.

#### **11.2.3.3. Vital Signs**

The mean change from Baseline to each scheduled assessment will be summarized descriptively by dosing regimen for each vital sign variable specified in this protocol.

Baseline will be defined as the last vital sign value obtained before the first dose of study drug on Day 1.

#### **11.2.3.4. Electrocardiogram**

The change from Baseline in electrocardiogram intervals (PR, QT, QTcF, QRS, and RR) to each scheduled assessment will be summarized descriptively by dosing regimen.

## **12. REGULATORY CONSIDERATIONS**

It is the responsibility of the clinical site and staff to notify the Sponsor and Sponsor's designee immediately upon becoming aware of a serious breach of GCP or of the study protocol. It is the responsibility of the Sponsor or its designee to notify appropriate regulatory authorities of any serious breach which is likely to effect, to a significant degree, the safety or mental integrity of the patients of the study or the scientific value of the study.

### **12.1. Good Clinical Practice**

The procedures set out in this study protocol pertaining to the conduct, evaluation, and documentation of this study are designed to ensure that the Sponsor, its authorized representative, and Investigator abide by GCP, as described in ICH Guideline E6(R2) and in accordance with the general ethical principles outlined in the Declaration of Helsinki. The study will receive approval from the EC prior to commencement. The Investigator will conduct all aspects of this study in accordance with applicable national, state, and local laws of the pertinent regulatory authorities.

### **12.2. Sponsor's Responsibilities**

The Sponsor or its designee is responsible for the following:

- Selecting qualified Investigators
- Providing Investigators with the information they need to properly conduct an investigation
- Ensuring proper monitoring of the investigation
- Ensuring that the applicable regulatory authorities, and all participating Investigators are properly informed of significant new information regarding adverse events or risks associated with the medication being studied

Before an investigational site can enter a patient into the study, a representative of the Sponsor will visit the investigational study site to:

- Determine the adequacy of the facilities
- Discuss with the Investigator(s) and other personnel their responsibilities with regard to protocol adherence, and the responsibilities of the Sponsor or its representatives. This will be documented in a Clinical Study Agreement between the Sponsor and the Institution/Investigator.

During the study, a monitor from Sun Pharmaceutical or its representative will have regular contacts with the investigational site, for the following:

- Provide information and support to the Investigator(s)
- Confirm that facilities remain acceptable
- Confirm that the investigational team is adhering to the protocol, that data are being accurately recorded in the case report forms, and that investigational product accountability checks are being performed
- Perform source data verification. This includes a comparison of the data in the case report forms with the patient's medical records at the hospital or practice, and other

records relevant to the study. This will require direct access to all original records for each patient (e.g., clinic charts).

- Due to the COVID-19 pandemic and the possibility for site closures and/or travel restrictions, source data verification may be performed remotely to the degree allowed per local regulations.

NOTE: If allowed per local regulations, remote source data verification will be instituted only during the COVID-19 pandemic. These are temporary measures that will be rescinded as soon as the rules governing the management of clinical trials during the COVID-19 pandemic are repealed.

- Record and report any protocol deviations.
- Confirm adverse events and serious adverse events have been properly documented on eCRFs and confirm any serious adverse events have been forwarded to the Sponsor and those serious adverse events that met criteria for reporting have been forwarded to the EC.

The monitor will be available between visits if the Investigator(s) or other staff needs information or advice.

As the Sponsor, Sun Pharmaceutical has delegated some responsibilities to a designee, or Contract Research Organization.

